3.3. Protocol deviations

For the allocation of patients to analysis populations, all protocol deviations will be reviewed according to the criteria specified below. A data review plan, which will be finalized prior to the data review meeting, might further specify the criteria. This plan will further specify all data and listings that are needed to review and assess the protocol deviations.

The determination of major and minor protocol deviations will be performed during the data review meeting and documented in the data review meeting minutes, which will be finalized prior to unblinding of the treatment group for the main analysis of data of the double-blind treatment period.

The following protocol violations are defined as major and will thus lead to the exclusion of a patient from the population:

Table 2. Protocol deviations

Number	Major protocol deviation	Reasons for exclusion from PP population
1	No valid assessment of PANSS at day -1 and week 4 (day 28)	X
2	Any violation than may have an impact on PANSS assessment	Х
3	Dose or administration of study medication deviates substantially from protocol schedule	Х

3.4. Changes from specifications in the protocol

Not applicable.

3.5. Interim analysis

No formal interim analysis is planned.

3.6. Timing of analysis

Baseline characteristic and efficacy analyses will be performed after the last subject completes a 28-day treatment period. All data until the Day 28 visit will be verified and locked before the unblinding. A safety analysis will be performed after all the data, including follow-up visits will be completed, verified and whole database will be locked.

4. Statistical analysis specifications

4.1. General

Due to exploratory nature of the study statistical significance level will be equal to 0.1. Based on provided assumption on the effect size this study is not sufficiently powered to reject the null hypothesis for the primary study endpoint at the more conventional significance level of 0.05. P-values ≥0.001 will be reported to 3 decimal places; p-values less than 0.001 will be reported as "<0.001". The mean, standard deviation, and any statistics other than quantiles, will be reported to one decimal place greater than the original data. Quantiles, such as median, or minimum and maximum will use the same number of decimal places as the original data. Estimated parameters, not on the same scale as raw observations (e.g. regression coefficients) will be reported to 3 significant figures.

4.1.1. Definitions/derived variables

Unless otherwise specified, baseline is defined as value collected closest but not later than time of the first IMP administration (Day 1). Values for following forms will be used as baseline:

• PANSS on Baseline (Day -1),

- CGI-S on Baseline (Day -1),
- BACS on Baseline (Day -1),
- ESRS on Baseline (Day -1),
- Vital signs pre dose (before IMP administration on Day 1),
- Clinical laboratory data (hematology, biochemistry, urinalysis, coagulation) on Day 1,
- 12-Lead ECG on Baseline (Day -1),
- PK blood sample collection [predose] on Day 1.

4.1.1.1. Day 1 and relative study days

Day 1 is defined as the day of the first administration of study medication (reference date). Reference date will include actual time of IMP administration. In general, any date provided in patient listings will be presented as study day (in addition to the date provided): If a date is later than the reference date then the study day is calculated as:

study day = date - reference date +1.

If a date is prior the reference date then the study day is a negative number calculated as

day = date - reference date.

Where applicable (such as classification of pre- vs concomitant medications) fractional part of the study day (i.e. including both date and time) will be used. Otherwise study days will be presented as integers.

4.1.1.2. BMI

BMI is calculated according to the equation:

BMI = weight [kg] / height [m]²

BMI will be subsequently categorized using following ranges:

<18.5 – Underweight

<18.5 - 25) - Normal weight

<25-30) — Overweight

≥30 – Obese.

4.1.1.3. Duration of disease

Duration of disease will be calculated as:

Duration of disease = (date of signature of ICF – date of initial diagnosis)/365.25, where ICF is Informed Consent Form.

For partial dates imputation described in section 4.1.5 will be used prior to duration calculation.

4.1.1.4. Duration of current exacerbation

Duration of current exacerbation will be calculated as:

Duration of current exacerbation = date of signature of ICF – start date of current exacerbation,

where ICF is Informed Consent Form.

For partial dates imputation described in section 4.1.5 will be used prior to duration calculation.

4.1.1.5. Treatment exposure and treatment compliance

Exposure to IMP will be calculated as:

Exposure = (Date of last IMP dose - Date of the first IMP dose) + 1

Extent of exposure will be calculated as a sum of exposures of all patients and expressed in patient-treatment years:

Extent of exposure [patient years] = sum(Exposure)/365.25.

4.1.1.6. Drug adherence

A subject is considered as a complier with dosing regimen when at least 80% (that is 23 out of 28 planned doses) of the IMP are compliant - meaning that patient took a full dose consisting of four capsules.

Drug adherence is defined as a number of capsules consumed divided by 112 (4 capsules per day in 28 days) or 4 multiplied by the number of days subject is in the study during the active period (if early terminated).

4.1.1.7. Positive and Negative Syndrome Scale (PANSS)

The PANSS is a 30-item scale used to measure symptoms of schizophrenia. The scale has 7 positive symptom items, 7 negative symptom items, and 16 general psychopathology symptom items. Each item is scored on a 7-point scale by the clinical rater based on a clinical interview with the patient. The efficacy assessment (PANSS) will be performed once at Screening; Baseline; on Days 1, 7, 14, 21 (before any other scale). Results of PANSS are calculated directly in the eCRF according to the formulas:

- Positive score: P1 + P2 + P3 + P4 + P5 + P6 + P7
- Negative score: N1 + N2 + N3 + N4 + N5 + N6 + N7
- Composite score: Positive score Negative score
- General: G1 + G2 + G3 + G4 + G5 + G6 + G7 + G8 + G9 + G10 + G11 + G12 + G13
 + G14 + G15 + G16
- Anergia: N1 + N2 + G7 + G10
- Thought Disturbance: P2 + P3 + P5 + G9
- Activation: P4 + G4 + G5
- Paranoid/Belligerence: P6 + P7 + G8
- Depression: G1 + G2 + G3 + G6
- Supplemental: P4 + P7 + G6 + S1 + S2 + S3
- Total score: Positive score + Negative score + General score

Where P = POSITIVE, N = NEGATIVE, G = GENERAL, S = SUPPLEMENTAL subsection of PANSS questionnaire.

Disease activity will be measured by PANSS Total Score and classified as low (PANSS <95) and high (PANSS >= 95).

Assessment of clinical responder will be performed based on the PANSS Total Score and is defined as a >= 30% decrease from baseline and calculated from the formula:

PANSS decrease = (PANSS at week X - PANSS at baseline)/(PANSS at baseline -30) * (-100%).

The adjustment of -30 points is due to the fact that PANSS total score ranges from 30 to 210 points. When unadjusted scores are used to calculate percentage change from baseline, it results in lower values of the percentage change, thus underestimating the response to the treatment and decreasing the proportion of responders (Leucht et al 2010).

4.1.1.7.1. Marder 5-factor model

For further analysis PANSS items will be used to create 5 new scores according to Marder 5-factor model (Hopkins, S.C., et al., 2018):

- Positive score = P1 + P3 + P5 + P6 + N7 + G1 + G9 + G12
- Negative score = N1 + N2 + N3 + N4 + N6 + G7 + G16
- Disorganized thoughts = P2 + N5 + G5 + G10 + G11 + G13 + G15
- Uncontrolled hostility/excitement = P4 + P7 + G8 + G14
- Anxiety/depression = G2 + G3 + G4 + G6

Where P = POSITIVE, N = NEGATIVE, G = GENERAL subsection of PANSS questionnaire.

4.1.1.8. Clinical Global Impression Scale – Severity (CGI-S)

The Clinical Global Impression (CGI) Scale is a standardized assessment tool that the Investigator can use to rate the severity of illness, change over time, and efficacy of medication, taking into account the patient's clinical condition and the severity of side effects. The CGI Scale consists of 3 global subscales formatted for use with the Global Scoring Sheet. The first subscale, Severity of Illness, assesses the Investigator's impression of the patient's current illness state. Scores on the Severity of Illness subscale range from 1 = not ill at all to 7 = among the most extremely ill. The efficacy assessment (CGI-S) will be performed once at Screening; Baseline; on Days 7, 14, 21 and 28 (after PANSS). Result of CGI-S will be analyzed numerically.

4.1.1.9. Clinical Global Impression Scale – Improvement (CGI-I)

Clinical Global Impression Scale - Improvement is a 7 points scale that requires the clinician to assess how much the patient's illness has improved or worsened relative to a baseline state at the beginning of the intervention. CGI-I will be performed on Days 7, 14, 21 and 28 (after PANSS and CGI-S). Result of CGI-S will be analyzed numerically.

Subject is to be considered as responder when rating is 1 = very much improved or 2 = much improved. Percentage of responders will also be shown.

4.1.1.10. Brief Assessment of Cognition in Schizophrenia (BACS)

The Brief Assessment of Cognition in Schizophrenia (BACS) is specifically designed to measure treatment-related improvements in cognition and includes alternate forms. BACS is a reliable and sensitive measure of cognitive function in schizophrenia. The BACS is a cognition assessment battery that assesses 6 domains of cognitive function found to be consistently impaired in schizophrenia: verbal memory, working memory, motor speed, attention, executive functions, and verbal fluency. Brief Assessment of Cognition in Schizophrenia will be performed at Baseline and on Days 14 and 28 (after PANSS, CGI-S and CGI-I). Raw scores are transferred to VeraSci where results are converted to T-Scores and based on that composite score is calculated and later transferred back according to the Data Transfer Agreement.

4.1.1.11. Extrapyramidal Symptom Rating Scale (ESRS)

The Extrapyramidal Symptom Rating Scale (ESRS) was developed to assess four types of drug-induced movement disorders (DIMD): Pakinsonism, akathisia, dystonia and tardive

dyskinesia (TD). It will be performed once at Screening (Day -10 to -2); once at Baseline (Day -1), once on Day 1, 7, 14, 21 and 28 when start of ratings is to be within 5 minutes before or after 2h post-dose (it will be performed after PANSS, CGI-S, CGI-I and BACS); once during the follow-up visits. A baseline assessment will be performed at Day -1 and repeated on days 7, 14, 21, 28 and follow-up visits. The ESRS consists of four subscales and four CGI-S scales:

- A questionnaire of EPS or DIMD (part I),
- An examination of Parkinsonism and akathisia (part II),
- An examination of dystonia (part III),
- An examination of dyskinesia (part IV),
- Clinical global impression severity (CGI-S) scales of tardive dyskinesia, Parkinsonism, dystonia and akathisia (part V – part VIII).

Total score for DIMD (Chouinard, G., Margolese, H.C., 2005) is formed based on all 41 items of the ESRS (part I – part IV), while CGI-S's are analyzed as separate items (part V – part VIII).

For the subjective examination (subscale I of the ESRS) scoring is on a 4-point scale (from 0 to 3). Rest of the DIMD examination (part II – part IV) is scored on a 7-point scale (from 0 to 6). Total score for DIMD is sum of the all 41 items from part I to part IV. For more details about scoring please refer to the table below.

Table 3. ESRS scoring

ESRS Part	Symptom	Scoring
Part I		Absent = 0
		Mild = 1
		Moderate = 2
		Severe = 3
Part II	Tremor	None = 0
		Borderline, occasional = 1
		Small amplitude, occasional = 2
		Small amplitude, frequent = 3
		Small amplitude, constant or almost so = 4
		Moderate amplitude, occasional = 3
		Moderate amplitude, frequent = 4
		Moderate amplitude, constant or almost so = 5
		Large amplitude, occasional = 4
		Large amplitude, frequent = 5
		Large amplitude, constant or almost so = 6
	Bradykinesia	Normal = 0
	,	Global impression of slowness in movements = 1
		Definite slowness in movements = 2
		Very mild difficulty in initiating movements = 3
		Mild to moderate difficulty in initiating movements = 4
		Difficulty in starting or stopping any movement, or freezing on initiating voluntary act
		= 5
		Rare voluntary movement, almost completely immobile = 6
	Gait and Posture	Normal = 0
		Mild decrease of pendular arm movement = 1
		Moderate decrease of pendular arm movement, normal steps = 2
		No pendular arm movement, head flexed, steps more or less normal = 3
		Stiff posture (neck, back) small step (shuffling gait) = 4
		More marked, festination or freezing on turning = 5
		Triple flexion, barely able to walk = 6
	Postural Stability	Normal = 0
		Hesitation when pushed but no retropulsion = 1
		Retropulsion but recovers unaided = 2
		Exaggerated retropulsion without falling = 3
		Absence of postural response would fall if not caught by examiner = 4
		Unstable while standing, even without pushing = 5
		Unable to stand without assistance = 6
	Rigidity	Normal muscle tone = 0
		Very mild, barely perceptible = 1

ESRS Part	Symptom	Scoring
		Mild (some resistance to passive movements) = 2
		Moderate (definite difficulty to move the limb) = 3
		Moderately severe (moderate resistance but still easy to move limb) = 4
		Severe (marked resistance with definite difficulty to move the limb) = 5
	Expressive Automatic	Extremely severe (limb nearly frozen) = 6 Normal = 0
	Movements	Very mild decrease in facial expressiveness = 1
	Wovements	Mild decrease in facial expressiveness = 2
		Rare spontaneous smile, decrease blinking, voice slightly monotonous = 3
		No spontaneous smile, staring gaze, low monotonous speech, mumbling = 4
		Marked facial mask, unable to frown, slurred speech = 5
		Extremely severe facial mask with unintelligible speech = 6
	Akathisia	Absent = 0
		Looks restless, nervous, impatient, uncomfortable = 1
		Needs to move at least one extremity = 2
		Often needs to move one extremity or to change position = 3
		Moves one extremity almost constantly if sitting, or stamps feet while standing = 4 Unable to sit down for more than a short period of time = 5
		Moves or walks constantly = 6
Part III		Absent = 0
		Very mild = 1
		Mild = 2
		Moderate = 3
		Moderately severe = 4
		Severe = 5
		Extremely severe = 6
Part IV	Lingual movements	None = 0
		Borderline = 1
		Clearly present, within oral cavity, occasional = 2
		Clearly present, within oral cavity, frequent = 3 Clearly present, within oral cavity, constant or almost so = 4
		With occasional partial protrusion, occasional = 3
		With occasional partial protrusion, frequent = 4
		With occasional partial protrusion, constant or almost so = 5
		With complete protrusion, occasional = 4
		With complete protrusion, frequent = 5
		With complete protrusion, constant or almost so = 6
	Jaw movements	None = 0
		Borderline = 1
		Clearly present, small amplitude, occasional = 2
		Clearly present, small amplitude, frequent = 3 Clearly present, small amplitude, constant or almost so = 4
		Moderate amplitude, but without mouth opening, occasional = 3
		Moderate amplitude, but without mouth opening, requent = 4
		Moderate amplitude, but without mouth opening, constant or almost so = 5
		Large amplitude with mouth opening, occasional = 4
		Large amplitude with mouth opening, frequent = 5
		Large amplitude with mouth opening, constant or almost so = 6
	Bucco-labial	None = 0
	movements	Borderline = 1
		Clearly present, small amplitude, occasional = 3
		Clearly present, small amplitude, frequent = 3
		Clearly present, small amplitude, constant or almost so = 4 Moderate amplitude, forward movement of lips, occasional = 4
		Moderate amplitude, forward movement of lips, focusional = 4
		Moderate amplitude, forward movement of lips, constant or almost so = 5
		Large amplitude, noisy smacking of lips, occasional = 5
		Large amplitude, noisy smacking of lips, frequent = 5
		Large amplitude, noisy smacking of lips, constant or almost so = 6
	Truncal movements	None = 0
		Borderline = 1
		Clearly present, small amplitude, occasional = 2
		Clearly present, small amplitude, frequent = 3
		Clearly present, small amplitude, constant or almost so = 4
		Moderate amplitude, occasional = 3
		Moderate amplitude, frequent = 4

ESRS Part	Symptom	Scoring
	. Vl	Moderate amplitude, constant or almost so = 5
		Greater amplitude, occasional = 4
		Greater amplitude, frequent = 5
		Greater amplitude, constant or almost so = 6
	Upper extremities	None = 0
	''	Borderline = 1
		Clearly present, small amplitude, movement of one limb, occasional = 2
		Clearly present, small amplitude, movement of one limb, frequent = 3
		Clearly present, small amplitude, movement of one limb, constant or almost so = 4
		Moderate amplitude, movement of one limb or movement of small amplitude involving
		two limbs, occasional = 3
		Moderate amplitude, movement of one limb or movement of small amplitude involving
		two limbs, frequent = 4
		Moderate amplitude, movement of one limb or movement of small amplitude involving
		two limbs, constant or almost so = 5
		Greater amplitude, movement involving two limbs, occasional = 4
		Greater amplitude, movement involving two limbs, frequent = 5
	1	Greater amplitude, movement involving two limbs, constant or almost so = 6
	Lower extremities	None = 0
		Borderline = 1
		Clearly present, small amplitude, movement of one limb, occasional = 2
		Clearly present, small amplitude, movement of one limb, frequent = 3
		Clearly present, small amplitude, movement of one limb, constant or almost so = 4
		Moderate amplitude, movement of one limb or movement of small amplitude involving two limbs, occasional = 3
		Moderate amplitude, movement of one limb or movement of small amplitude involving
		two limbs, frequent = 4
		Moderate amplitude, movement of one limb or movement of small amplitude involving
		two limbs, constant or almost so = 5
		Greater amplitude, movement involving two limbs, occasional = 4
		Greater amplitude, movement involving two limbs, frequent = 5
		Greater amplitude, movement involving two limbs, constant or almost so = 6
	Other involuntary	None = 0
	movements	Borderline = 1
		Clearly present, small amplitude, occasional = 2
		Clearly present, small amplitude, frequent = 3
		Clearly present, small amplitude, constant or almost so = 4
		Moderate amplitude, occasional = 3
		Moderate amplitude, frequent = 4
		Moderate amplitude, constat or almost so = 5
		Greater amplitude, occasional = 4
		Greater amplitude, frequent = 5
B ()/ B ()///		Greater amplitude, constant or almost so = 6
Part V – Part VIII		Absent = 0
		Borderline = 1
		Very mild = 2
		Mild to moderate difficulty in initiating movements = 3 Moderate = 4
		Moderately severe = 5 Marked = 6
		Severe = 7
		Extremely severe = 8
	 	Laudinery 304016 - 0

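### SAP Table 3 scores bucco-labial movements on a different grid from the other six Part IV items and cannot give a 2, contrary to the SAP's own 0-to-6 scale

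*SAP*

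**What the plan says.** SAP 4.1.1.11 states that items in parts II to IV are scored on seven points, 0 to 6. The total for drug-induced movement disorders adds all 41 items of parts I to IV. The section cites the ESRS manual where it introduces that total and sends the reader to Table 3 for scoring detail.

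For bucco-labial movements, Table 3 gives:

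- Small amplitude: "Clearly present, small amplitude, occasional = 3" and "Clearly present, small amplitude, frequent = 3".
- Moderate amplitude: "Moderate amplitude, forward movement of lips, occasional = 4", then "Moderate amplitude, forward movement of lips, focusional = 4". The second label is garbled in the text as read from the PDF; its position and value fit the frequent category.
- Large amplitude: "Large amplitude, noisy smacking of lips, occasional = 5" and "Large amplitude, noisy smacking of lips, frequent = 5".

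For jaw and truncal movements, the corresponding first cell is "Clearly present, small amplitude, occasional = 2", with frequent one point higher.

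In the rows for Parts V to VIII (the global severity ratings), level 3 reads "Mild to moderate difficulty in initiating movements = 3". The SAP analyses these ratings as separate items, outside the 41-item total.

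ESRS monitoring is a secondary safety endpoint (Protocol 3.3.2, SAP 2.2.2.2). Protocol 10.11.6 and SAP 4.8.3.5 plan descriptive statistics of the score and its change from baseline, and SAP 4.8.3.5 adds boxplots.

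**The concern.** One row of a scoring table departs from its six sister rows without explanation, and it conflicts with the section's own statement of the item's range. A programmer who takes Table 3 literally would score any occasional bucco-labial movement one point above the common pattern. The same programmer would record no change when a patient moves between occasional and frequent at the same amplitude.

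Movement disorders are worth scoring correctly here. Protocol 2.5 reports, for another PDE10A inhibitor, akathisia in 13.3% against 4.9% on placebo and dystonia in 6.0% against 1.2%. The route from Table 3 to the analysed score is also open. For PANSS, SAP 4.1.1.7 says the results are computed in the eCRF; for the ESRS the SAP makes no such statement.

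**Working it through.** **Inputs.** All cell values come from SAP Table 3. The item range and the 41-item sum come from the text of SAP 4.1.1.11. The 55 patients per group comes from SAP 2.4. Every item below also has none = 0 and borderline = 1.

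**Step 1: compare the grids.** Cells are occasional/frequent/constant.

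| Item | Lowest amplitude | Middle | Highest | Reachable scores |
|---|---|---|---|---|
| Lingual, jaw, truncal, upper extremities, lower extremities, other (Part IV); tremor (Part II) | 2/3/4 | 3/4/5 | 4/5/6 | 0, 1, 2, 3, 4, 5, 6 |
| Bucco-labial (Part IV) | 3/3/4 | 4/4/5 | 5/5/6 | 0, 1, 3, 4, 5, 6 |
| Difference | +1/0/0 | +1/0/0 | +1/0/0 | |

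**Step 2: reproduce the plan's figure.** The stated seven levels are reproduced for the six sister items and tremor. For the bucco-labial item the count is six, with no 2. Occasional and frequent tie at all three amplitudes in this row, and at none in the others.

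**Step 3: effect on one patient, taking the common grid as correct (an assumption).** Let e = 1 if the bucco-labial rating at a visit is occasional, at any amplitude, and e = 0 otherwise.

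- Total from Table 3 minus total from the common grid = e, so 0 or +1.
- Error in change from baseline = e(visit) − e(baseline), so −1, 0 or +1.

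| Baseline to visit (small amplitude) | Change, Table 3 | Change, common grid | Error |
|---|---|---|---|
| None to occasional | 3 − 0 = 3 | 2 − 0 = 2 | +1 |
| Occasional to frequent | 3 − 3 = 0 | 3 − 2 = 1 | −1 |
| Occasional to none | 0 − 3 = −3 | 0 − 2 = −2 | −1 |
| Occasional to occasional | 0 | 0 | 0 |
| None to frequent | 3 − 0 = 3 | 3 − 0 = 3 | 0 |

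**Step 4: effect on a group mean.** If k of 55 patients in an arm are rated occasional at a visit, the mean total rises by k/55. The documents give no value for k, so these are illustrations: k = 1 gives 1/55 = 0.018 points, and k = 5 gives 5/55 = 0.091 points. The ceiling is 1 point, if all 55 were rated occasional. The difference between two arms of 55 moves by (k₁ − k₂)/55.

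**Step 5: the Part V to VIII label.** The text at level 3 repeats the wording that Part II gives to bradykinesia at score 4. It stands between very mild (2) and moderate (4) on a severity scale that also rates tardive dyskinesia, dystonia and akathisia. The numeric level 3 is intact and no score changes.

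**The case against.** A reader might infer that the ESRS total is wrong. The documents do not support that. It would require that the manual uses the common grid for this item, and that the analysed score comes from Table 3 rather than from a number entered by the rater. The manual was not available for this review, and the SAP is silent on the second point. It ties the total to the manual and offers Table 3 only for further detail. A row that differs from its neighbours is a reason to query it, not proof of error. This stands, and it limits the conclusion to a conditional one.

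Three further inferences also fail:

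- **Distorted shift tables.** No ESRS shift analysis is planned; shifts are specified for laboratory data, vital signs, ECG and C-SSRS.
- **Only the mildest movements affected.** The cells concerned are occasional at all three amplitudes, and borderline keeps its score of 1.
- **Onset missed or created.** None to occasional is an increase on either grid, and no ESRS onset rule or threshold is defined.

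The practical effect is also likely to be small. Exclusion criterion 11 covers tardive dyskinesia and other chronic movement disorders that may interfere with interpretation, treatment lasts 28 days, and the events reported for the other PDE10A inhibitor in Protocol 2.5 do not include bucco-labial dyskinesia.

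A misread of the PDF could be suggested, since labels near both places are corrupted. For the bucco-labial row it is implausible: three separate digits are each higher by 1 in the same position. For the Part V to VIII label it cannot be excluded, so that point remains a separate check.

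**Conclusion.** Table 3 and the text of SAP 4.1.1.11 contradict each other. A seven-point item running from 0 to 6 cannot lack a 2, and this needs no outside source. The consistent +1 in the occasional cells makes a transcription slip the likely explanation, but the manual has to settle it.

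If the common grid is right and Table 3 generates the score, each occasional bucco-labial rating adds 1 point to the 41-item total. Change from baseline is then off by at most 1 point in either direction, and arm means move by k/55. If either condition fails, the analysed score is unaffected and only the document needs correcting or annotating. The planned ESRS analysis is descriptive, so no test, power figure or significance level depends on it, and no efficacy result is touched. This is a minor point, but the scoring rule should not stay as written.

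**What to change.** Before unblinding:

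1. Check the bucco-labial row against the cited ESRS manual, and establish whether analysed scores are entered by the rater, computed in the eCRF or recoded from Table 3. State the answer in SAP 4.1.1.11.
2. Unless the manual prints the row as it stands, set the three occasional cells to 2, 3 and 4, and confirm that neither the eCRF nor the analysis programs used the printed values.
3. If the manual does print the row this way, keep it and note the exception to the seven-point statement.
4. Separately, check the level 3 label in Parts V to VIII and replace it with the manual's severity grade.

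Timing matters because SAP 3.6 runs the safety analysis after the Day 28 data have been unblinded for efficacy. A scoring rule revised between those two points would be revised with treatment known.

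The cost is at most four table cells (three scores and one label), or an exception note in place of the three scores, plus one check of the eCRF coding and programs.
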